11.3.5.2 Investigator's Global Assessment

Descriptive statistics will be provided for the investigator's global assessment of disease severity in the treatment area, presented by treatment and visit.

Descriptive statistics will show frequencies for each score.

11.3.6 Analysis of Exploratory Endpoints

11.3.6.1 Lesion counts by clinical evaluation.

Descriptive statistics will be provided for inflammatory, non-inflammatory and their sum by treatment and visit for data obtained by clinical assessment.

Descriptive statistics will include means, standard deviations, median and ranges. Furthermore mean curves over time will be made.

11.3.6.2 Treatment success according to IGA

Rates of treatment success, defined as at least a two grade improvement in IGA at week 12 compared to baseline, will be compared between treatments using Fisher's exact test.

11.3.6.3 Inflammatory cytokine expression

Descriptive statistics will be presented showing means, standard deviations medians and ranges by treatment and time point. The results will also be shown as box-plots.

If applicable data will be log transformed before deriving descriptive statistics.

11.3.6.4 Microbiome profile

The analysis of data relating to the microbiome will be specified in a separate analysis plan, and the reporting will be done separately.

11.3.6.5 Subject evaluation of Acne QoL

Descriptive statistics will be provided for the subject's evaluation of Acne QoL at Day 1 and Week 12 for the total and each of the four domains contained within the questionnaire (self-perception, role-social, role-emotional and acne symptoms).

11.3.6.6 Subject evaluation of TSQM II

Descriptive statistics will be provided for the subject's evaluation of TSQM II at Week 12 for the total and each of the four domains contained within the questionnaire (effectiveness, side effects, convenience and global satisfaction).

11.3.6.7 Subject Global Cosmetic Score

Descriptive statistics will be presented for the Subject's Global Cosmetic Score at Week 12 showing means, standard deviations medians and ranges by treatment.

11.3.7 Analysis of Safety

The analysis of safety will be based on the safety analysis set.

11.3.8 Adverse Events

Treatment emergent adverse events, i.e. with an onset or intensifying after treatment start will be coded according to MedDRA v19.0 summarised by the following tables showing event counts, incidences and incident rates:

- An overall summary showing statistics for all AEs, serious AE's, AE's with actions taken, AE's stratified by severity, related AE's by treatment, cutaneous AE's by treatment
- AE by system organ class and preferred term
- AE's by system organ class and preferred term stratified by disease severity
- Related AE's by system organ class and preferred term by treatment
- Cutaneous AE's by system organ class and preferred term by treatment
- Serious adverse events will be evaluated separately and a narrative for each will be given.
- AEs leading to withdrawal from trial or discontinuation of investigational product will be listed.

11.3.9 Other Specific Safety Assessments

11.3.9.1 Composite and component LSR score

The incidence and grade of LSRs will be summarised by treatment and time point. LSR grades will be summarised by descriptive statistics including mean, standard deviation, median and range as well as frequency counts by treatment for each of the six individual LSRs: erythema, flaking/scaling, crusting, swelling, vesiculation/pustulation, and erosion/ulceration. LSRs leading to withdrawal from trial and/or withdrawal of IP will be tabulated.

A composite (sum) score will be obtained by summing the six individual component LSR scores (range 0-24) at each visit (Visit 2 to 10). The composite score and change from baseline will be summarised by treatment group at each visit using descriptive statistics. The maximum composite LSR score across visits and the visits of occurrence of the maximum composite LSR score will be tabulated by treatment. After the maximum is attained, the first visit where the composite LSR score is less than or equal to the composite score at baseline will be tabulated by treatment group.

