5.2 Secondary Endpoints

- Inflammatory lesion count in the treatment area for LEO 43204 gel and vehicle gel at Week 12.
- Non-inflammatory lesion count in the treatment area for LEO 43204 gel and vehicle gel at Week 12.
- Investigator's Global Assessment of the treatment area for LEO 43204 gel and vehicle gel at Week 12.
- Composite and component LSR score at all visits
- Occurrence of unacceptable LSR scores or unacceptable safety and tolerability events at all visits (as described in section 12)

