8.1 Schedule of Trial Procedures

	Screening Visit (SV) Day 0	Day 1	Day 2	Day 3	Day 4	Day 8	Week 2	Week 4	Week 8	Week 12
Visit number	1	2*	3	4	5	6	7	8	9	10
Visit window	Day -28 to Day 1						±3 Days	±3 Days	±5 Days	±1 Week
Informed consent	x									
In-/exclusion criteria ¹⁾	x	x								
Subject demographics	x									
Subject height and weight	x									
Identification of Treatment Areas (TA)	x	x	x	x	x	x	x	x	x	x
Medical history and concurrent diagnosis	x									
Acne Treatment History	x									
Concomitant medication	x	x	x	x	x	x	x	x	x	x
Abbreviated physical examination	x									x
Vital signs	x									x
Urine pregnancy test	x	x ¹⁾					x	x	x	x
Clinical assessments of full face IGA	x									
Clinical assessments of TA _{left} and TA _{right} for IGA and lesion count	x	x					x	x	x	x
Photos (cohort 1,2 and 3)		x	x	x	x	x	x	x	x	x
Photos (only cohort 3 and 4)	x									
Subject questionnaire AcneQoL		x								x
Subject questionnaire TSQM II										x
Subjects Global Cosmetic Score										x
Tape lift for inflammatory biomarker analysis ⁴⁾		x					x	x	x	x

Swab for microbiome collection ⁴⁾		x					x	x	x	x
Randomisation		x								
Administration of trial medication by site staff		x	x**	x**						
LSR evaluation		x	x	x	x	x ²⁾	x	x	x	x
Adverse Events		x	x	x	x	x	x	x	x	x
Phone Call						x ³⁾				
End of Trial Form										x

1) For women of child-bearing potential a urine pregnancy test must be performed, prior to treatment.

2) Not applicable for cohort 4

3) Only applicable for cohort 4

4) Not applicable for cohort 1

* Can be performed the same day as Screening

** Treatment on Day 2 and/or 3 is optional as described in section 6.1.

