8.13 Other Safety Assessments

Local Skin Responses (LSRs)

Assessment of local skin responses in the treatment areas using the LSR Grading Scale will be performed at Day 1 prior to first IP application and at all subsequent visits as indicated in section [8.1](#).

Local skin responses are defined as erythema, flaking/scaling, crusting, swelling, vesiculation/pustulation and erosion/ulceration. The presence/absence and grade of each LSR will be recorded using the LSR Grading Scale shown in [Appendix 6](#). This grading scale will also be provided as hard copy to the site. Any local skin responses identified within the treatment area which do not match the criteria in the LSR Grading Scale should be reported as AEs.

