8.15 Investigator Assessments

The investigator assessments will be conducted by an experienced and qualified dermatologist. All assessments of each subject at the site should preferably be performed by the same dermatologist. At Visit 1, identification of the treatment area should be documented on an individual transparent film using three-point landmark technique (refer to [Appendix 10](#)

for details). At all subsequent visits, the transparent film should be used to locate the treatment area for further treatment or assessments of the treated skin.

The following clinical assessments must be made at visits as specified in section 8.1:

1. IGA of the full face (see Table 4 for grading) at Screening to determine acne vulgaris severity for inclusion to the trial at Screening.
2. IGA and non-inflammatory lesion count (open and closed comedones), and inflammatory lesion count (erythematous papules and pustules) in TA_{left} and TA_{right} at Screening and Day 1, Week 2, 4, 8, and 12.
3. LSR assessments (see 8.13) in TA_{left} and TA_{right} using the LSR Grading Scale at Day 1 prior to IP application, and on all subsequent site visits.
4. Skin photography at Day 1, prior to treatment, and on all subsequent site visits (only for cohort 1, 2, and 3).
5. Skin photography at screening for cohort 3 and 4
6. All other skin findings than LSRs and acne will be reported as medical history at Screening or as AEs at subsequent visits.
7. Biomarker and microbiome samplings in Cohort 2, 3 and 4 at Day 1 and at Week 2, 4, 8 and 12. See [Appendix 2](#) and [Appendix 4](#). Samples will be stored for later analysis.

Table 4. Investigator's Global Assessment Scale for Acne Vulgaris*

Grade	Description
0	Clear skin with no inflammatory and non-inflammatory lesions
1	Almost clear; rare non-inflammatory lesions with no more than one small inflammatory lesion
2	Mild severity; greater than Grade 1; some non-inflammatory lesions with no more than a few inflammatory lesions (papules/pustules only, no nodular lesions)
3	Moderate severity; greater than Grade 2; up to many non-inflammatory lesions and may have some inflammatory lesions, but no more than one small nodular lesions
4	Severe; greater than Grade 3; up to many non-inflammatory and inflammatory lesions, but no more than a few nodular lesions

*The same scale will be used for full face and TA evaluation of IGA.

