4.4.2 Other safety endpoints

Vital signs will be presented as described in the protocol.

5 Programming and Quality Control

SDTM data sets are received from the data management provider Novella (formerly TKL). Larix will review the SDTMs and inform Novella and Leo of any deficiencies and discrepancies.

Larix will prepare ADaM data sets, ADRG and define file. ADaM data sets will be QCed by double programming.

Tables, listings and figures will be independently code reviewed by a qualified programmer (statistician for analysis programs) according to Larix SOPs.

ADaM data sets, tables, listings and figures will be produced by SAS ver. 9.4 following Larix' SOPs on programming.

6 Tables, Listings and Figures

The table shells are presented in a separate document.

The following figures will be prepared:

1. Mean and individual lesion count profiles
2. Plots of mean and individual profiles of composite LSRs by visit and lateral side
3. Plots of mean and individual profiles of maximum of right and left side composite LSRs by visit

All data will be listed by subject, visit and treatment (if relevant).

7 Change Log

| Edition | Effective on | Reason for revision |
|---------|--------------|---------------------|
| 1.0 | 19MAY2017 | New version |

Signature Page for TMF-000020290 v1.0

| | |
|------------------------------|--|
| Reason for signing: Approved | Management / Lead Approver Verdict(s) Name: PPD Capacity: Biostatistics Date of signature: 31-Aug-2017 07:36:20 GMT+0000 |
|------------------------------|--|

| | |
|------------------------------|--|
| Reason for signing: Approved | Approver Verdict(s) Name: PPD Capacity: Quality Control Date of signature: 31-Aug-2017 08:22:26 GMT+0000 |
|------------------------------|--|

Signature Page for TMF-000020290 v1.0

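### The maximum composite LSR may be the pre-dose score, and the return-to-baseline table requires no rise, so cheeks that never reacted are mixed with cheeks that recovered (minor)

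*Protocol*

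**What the plan says.** Protocol section 11.3.9.1 builds the composite by "summing the six individual component LSR scores (range 0-24) at each visit (Visit 2 to 10". Two tabulations follow. The first is the size and timing of the peak: "The maximum composite LSR score across visits and the visits of occurrence of the maximum composite LSR score will be tabulated by treatment". The second, by treatment group, is the recovery visit: "After the maximum is attained, the first visit where the composite LSR score is less than or equal to the composite score at baseline".

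Visit 2 is Day 1 in the schedule (section 8.1). Section 8.13 says LSR grading "will be performed at Day 1 prior to first IP application and at all subsequent visits", and section 8.15 agrees: "using the LSR Grading Scale at Day 1 prior to IP application, and on all subsequent site visits". The Visit 2 composite is therefore a pre-dose score. It serves as the baseline and is also one of the values over which the maximum is taken.

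The listed secondary endpoint (section 5.2) is "Composite and component LSR score at all visits". The SAP text available does not redefine the maximum or the return visit. SAP section 6 states: "The table shells are presented in a separate document".

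**The concern.** A table of peak reaction and visit of recovery should describe what happened after the gel was applied. Here a score recorded before exposure can be reported as the peak for a treatment. A cheek also needs no reaction to receive an entry in the recovery table.

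The protocol says in sections 3.3.1 and 3.4 that it is unknown whether the LSR profile in young adults with acne will resemble that seen in actinic keratosis. The size and duration of the reaction are therefore real questions for this trial. If non-reacting cheeks sit in the same rows as early recoveries, a reader comparing the two treatment columns cannot tell an absent reaction from a short one.

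**Working it through.** The plan gives no figure for this point beyond the composite range, which reproduces: 6 components × maximum grade 4 = 24.

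**Inputs.** Composite at Visits 2 to 10, maximum over those visits, and the return rule (section 11.3.9.1); Visit 2 graded pre-dose (sections 8.13 and 8.15); Visit 3 = Day 2 (section 8.1). Cohort 4 has no Day 8 grading (section 8.1, footnote to the LSR row: "Not applicable for cohort 4"). That does not matter here, because Day 2 is graded in every cohort.

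**General argument.** Let b be the Visit 2 composite, s(v) the composite at Visits v = 3 to 10, and M = max{b, s(3), ..., s(10)}. Assume the gradings are complete.

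- All s(v) < b: M = b, attained only at Visit 2. The first later visit with s(v) ≤ b is Visit 3, i.e. Day 2, under any tie rule.
- Highest s(v) = b: M = b, attained at Visit 2 and at each tied visit. Counting from the first occurrence gives Day 2. Counting from the last gives the next graded visit after the final tie, or none if that tie is at Week 12.
- Some s(v) > b: M is attained post-dose only, and Visit 2 plays no part in the maximum.

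**Constructed records** (order: Day 1 pre-dose, Days 2, 3, 4 and 8, Weeks 2, 4, 8 and 12):

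| Record | Maximum | Visit(s) of maximum | Return, first occurrence | Return, last occurrence | Under the fix |
|---|---|---|---|---|---|
| A: 3,2,2,2,2,1,1,1,1 | 3 | Day 1 pre-dose | Day 2 | Day 2 | no increase |
| B: 0 at all nine | 0 | all nine | Day 2 | none | no increase |
| C: 2,1,1,1,1,1,1,1,2 | 2 | Day 1 pre-dose, Week 12 | Day 2 | none | no increase |
| D: 1,5,8,9,5,1,1,0,0 | 9 | Day 4 | Week 2 | Week 2 | Week 2 |
| E: 1,1,1,2,1,1,1,1,1 | 2 | Day 4 | Day 8 | Day 8 | Day 8 |

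Records A to C never rise, yet A always receives a recovery visit, and B and C do so under one tie convention. Records D and E rise, and the fix leaves their results unchanged.

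**Limiting the maximum to Visit 3 onward is not enough.** With first occurrence, record B then peaks on Day 2 and returns on Day 3. Record A has maximum 2, first on Day 2, and also returns on Day 3. The condition that the score exceeded baseline is needed as well.

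**How many cheeks.** The documents do not say how many vehicle cheeks show no rise. The safety set is drawn from a full analysis set of 38 (section 11.2), so at most 38 vehicle cheeks are involved. If the non-rising share were anywhere from 10% to 90%, 38 × 0.1 = 3.8 and 38 × 0.9 = 34.2, i.e. about 4 to 34 cheeks. That range is purely an assumption. For tied cheeks it also needs the first-occurrence reading to place them on Day 2.

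**The case against.** A reader might infer that every non-reacting cheek is bound to be reported as peaking before dosing and recovering on Day 2. The documents do not support that. Section 11.3.9.1 speaks of visits of occurrence in the plural and states no tie rule. A flat cheek could be listed at all nine visits, or under a last-occurrence convention receive no return visit. Only cheeks strictly below baseline at every later visit are fixed at Day 2. A firm count of affected vehicle cheeks is likewise not available from the documents.

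A reader might also infer that a secondary endpoint is compromised. It is not. The endpoint in section 5.2 is the score at all visits. The maximum and the return visit are supplementary descriptive tabulations with no test attached. The Safety Review Committee criteria in section 12 use component grades and the investigator's judgement, not these tables.

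Three further points on the other side have weight:

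- The plan does not call the tabulated visit a resolution. For a non-reactor, Day 2 is a true statement about being at or below baseline.
- Change from baseline by visit (section 11.3.9.1), the individual profile plots and the data listings (SAP section 6) let a careful reader separate the two groups.
- Section 10.3.1 cites mean maximum facial composites of 8.9 and 10.6 with active gel in actinic keratosis. If acne skin responds similarly, few active cheeks will fail to rise.

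The table shells are also not among the documents and could contain a restriction.

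These points limit the consequence and lower the severity. They do not remove the defect, because no tie convention makes the rule as written identify a cheek with no reaction.

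**Conclusion.** The point stands and is minor. As written, a pre-dose score can be the maximum attributed to a treatment, and cheeks that never rose enter the same return table as cheeks that reacted and recovered. This is certain for cheeks below baseline at every later visit. For cheeks that only tie baseline, the result depends on an unstated tie rule.

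The mixing probably falls more on the vehicle column. That rests on the assumption that vehicle reacts less than active gel. The share affected is unknown.

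The damage is confined to the descriptive visit-of-maximum and return tables, plus the reported maximum of cheeks that stayed below baseline (record A: 3 pre-dose, against a post-dose maximum of 2). The primary analysis, the committee's criteria and the maximum of any cheek that rises above baseline are unaffected. The conclusion also assumes that the unseen table shells do not already restrict the derivation. If they do, it remains only to state that rule in the SAP.

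**What to change.** State in the SAP, as a clarification of protocol section 11.3.9.1, and carry into the table shells:

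1. The maximum composite LSR is taken over post-dose gradings, Visit 3 onward.
2. The first return visit is tabulated only for cheeks whose post-dose maximum exceeds the Day 1 pre-dose score.
3. All other cheeks appear by treatment in a separate row, labelled as no increase over baseline.
4. Where the maximum is tied, the first post-dose visit at which it occurs is used.

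The cost is a few sentences and a small programming change, with no new data. The one downside is a smaller denominator in the return table, probably most visible for vehicle. The new row makes that reduction explicit.

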11.3.9.2 Vital Signs and Physical Findings

Observed values and changes from baseline in vital signs blood pressure, heart rate, will be summarised as mean, standard deviation (SD), median, minimum and maximum values.

Clinically relevant physical findings will be reported as medical history or AEs as applicable.

11.3.9.3 Clinical Laboratory Evaluation

Not applicable

11.3.10 Interim Analysis

After Week 2 (Visit 7) for specified number of subjects (refer to section 6.1) along the course of the trial analyses of blinded data will be performed evaluating the safety profile and the LSRs (refer to section 12).

The analyses will include:

- List of adverse event, using investigators term
- Number of subjects with:

One of the following scores on the LSR scale at any time:

- Grade 4 crusting
- Grade 4 erosion / ulceration
- Grade 4 vesiculation / pustulation extending significantly outside the treatment area

Or two or more of the following scores on the LSR scale at any time:

- Grade 4 erythema
 - Grade 3 crusting
 - Grade 4 swelling extending significantly outside the treatment area
 - Grade 3 erosion / ulceration
 - Grade 3 vesiculation / pustulation
- Descriptive statistics of composite and components of LSRs by visit and lateral side
 - Plots of mean and individual profiles of composite LSRs by visit and lateral side
 - Descriptive statistics of maximum of right and left side composite and component LSRs by visit

- Plots of mean and individual profiles of maximum of right and left side composite LSRs by visit
- List of individual component LSRs

11.3.11 General Principles

All significance tests will be two-sided using the 5% significance level. All confidence intervals will be presented with 95% degree of confidence.

An observed cases approach will be used for tabulations of data by visit (i.e. involving only those subjects who attended each specific visit).

Categorical data will be summarised using the number and percentage of subjects in each category. Continuous data will be summarised using the mean, median, standard deviation (SD), minimum and maximum values.

Any changes from the statistical analysis planned in this clinical trial protocol will be described and justified in a protocol amendment or the statistical analysis plan update and/or in the clinical trial report dependent on the type of deviation.

11.3.12 Handling of Missing Values

Subjects with missing counts of inflammatory and non-inflammatory lesions at visits 7, 8 and 9 (weeks 2, 4 and 8) will be excluded from the analyses based on FAS and PP for these time points, and missing lesion counts will therefore not be imputed for these subjects. For subjects with missing lesion counts at visit 10 (week 12), the missing lesion counts of visit 10 will be imputed and the endpoints will be derived afterwards from the imputed values.

A multiple imputation method will be used to handle missing data. The imputation method relies on the assumption that the missing data are missing at random (MAR), i.e. the probability that an observation is missing can depend on observed data but is unrelated to the data not observed. All imputations will be performed by lesion type and treatment group.

Imputation of missing values for subjects with a monotone missing data pattern (i.e. there exist a time point for the subject where all observations before the time point are present and all later observations are missing) will be based on the full observed dataset excluding subjects with a non-monotone missing data pattern. The missing values for lesion counts at visit 10 will be imputed sequentially from a linear regression model with lesion counts at previous visits as covariates and treatment compliance (as identified by means of protocol deviations) as factor.

For subjects with a non-monotone missing data pattern, the lesion counts at visit 10 will be imputed using data from subjects without a non-monotone missing data pattern based on the Markov Chain Monte Carlo (MCMC) method including compliance effect, and lesion counts at previous visits 7, 8 and 9 as continuous variables. In case of non-convergence the compliance effect will be excluded from the imputation model. The imputed values at visit 10 will be rounded to the nearest non-negative integer.

Table 5 shows seed and numbers of imputations used for the multiple imputations

Sensitivity analyses of the method of handling missing data will be performed for the analyses of the imputed endpoints: last observation carried forward (LOCF) and an observed cases approach.

Table 5 Parameters defining imputation of lesion counts

Assessment	Seeds for Imputation for subjects with monotone pattern of missing data	Seeds for Imputation for subjects with non-monotone pattern of missing data	Number of imputations
Inflammatory lesions	255951	897661	100
Non-inflammatory lesions	477345	657616	100

12 Trial Committees

The Safety Review Committee will comprise the following members:

- The International Coordinating Investigator
- Sponsor's medical expert
- Sponsor's Head of Translational Medicine
- Sponsor's pharmacovigilance expert
- Sponsor's Statistician
- The ICTM

Primary functions of the Committee:

- Operate to written procedures defined by the Safety Review Committee Charter for the trial.
- Document decision in the meeting minutes.

- Convene to review safety and tolerability after the last subject in cohort 1, 2 and 3 has completed the Week 2 follow-up visit (Visit 7).
- Decide whether quality of data is sufficient and whether unacceptable LSRs, safety or tolerability events have occurred necessitating termination of the clinical trial.

Prior to dosing of the first subject, the Safety Review Committee Charter will be finalised detailing the evaluation procedure and processes for immediate communication between sites.

Unacceptable LSR scores, safety and tolerability events:

Unacceptable safety and tolerability events in an individual subject are defined as 1) clinically relevant signs or symptoms observed, which in the opinion of the investigator are deemed unacceptable or 2) one or more of the following LSRs:

- Grade 4 crusting
- Grade 4 erosion / ulceration
- Grade 4 vesiculation / pustulation extending significantly outside the treatment area

Or two or more of the following:

- Grade 4 erythema
- Grade 3 crusting
- Grade 4 swelling extending significantly outside the treatment area
- Grade 3 erosion / ulceration
- Grade 3 vesiculation / pustulation

Criteria for terminating the trial:

The trial will be terminated if the perception of the benefit/risk ratio (judged from clinical symptoms, signs and/or (S)AEs) becomes unfavorable for the continuation of the trial.

- Any decision regarding premature termination of the entire trial will be made after mutual agreement between the Investigator and the sponsor.
- The sponsor reserves the right to cancel the trial at any time
- Due to the design of the trial, there are no statistical criteria for trial termination.
- The cumulative frequencies of subjects with unacceptable LSRs, safety and tolerability events (as defined above) that will strongly support the decision for trial termination are:

- 2 out of 3 subjects with unacceptable LSRs, safety and tolerability events after Cohort 1
- 3 out of 9 subjects with unacceptable LSRs, safety and tolerability events after Cohort 2 (cumulative)
- 5 out of 15 subjects with unacceptable LSRs, safety and tolerability events after Cohort 3 (cumulative)

13 Electronic Case Report Forms and Data Handling

